7.4.10. Karnofsky Performance Status

Karnofsky Performance Status (KPS) score will be summarized using descriptive statistics and listed at each time point assessed. A stacked bar chart illustrating the distribution of KPS scores at baseline, 3 months, 6 months, 9 months, and 12 months post first therapeutic dose will be provided for the Full Analysis Set.

7.4.11. Overall Survival

Overall survival (OS) is defined as the time from the date of first therapeutic dose to the date of death from any cause. OS time will be censored at the last date the subject is known to be alive. The Kaplan-Meier predicted survival rates at Years 1-5 will be reported. Overall survival will be listed and Kaplan-Meier curves will be prepared. The last date that the patient was confirmed to be alive will be obtained from information reported by the clinical site: if this information is collected outside of the CRF the last date the subject is known to be alive or date of death reported from the site will be provided in a spreadsheet and integrated into analysis datasets.

Overall survival will also be presented by primary endpoint status.

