7. STATISTICAL METHODS

Standard descriptive statistics will be presented for data collected. For continuous measures, the mean, standard deviation (SD), median, range and sample size (N) will be presented; for categorical measures, frequency distributions including the number of subjects and percentages in each category will be presented. Correlations between outcomes will be computed and presented as appropriate (e.g., between levels of different tumor markers). Time-to-event data will be summarized using Kaplan-Meier methodology using 25th, 50th (median), and 75th percentiles with associated two-sided 95% confidence intervals, as well as percentage of censored observations.

Numbering for tables and listings will follow the following convention: tables will be numbered 14.x.x.x and listings will be numbered 16.2.x.x.x.

Additional descriptive or inferential analyses not described in this document will be performed on an ad hoc basis.

For the purpose of calculation of the primary endpoint and tumor marker reporting, a month is defined as 28 days to be consistent with the visit schedule. For the purposes of defining the 12-month efficacy period in which the primary endpoint benefit could begin, this period is 12 calendar months. For the calculation of overall survival using Kaplan-Meier methods, a month will be defined as a calendar month or 30.25 days to approximate calendar time.

For each study variable of interest, the subsections that follow provide: when and how it is to be measured; whether it will be summarized in a table, included in listings or displayed in figures; what additional statistical analyses, if any, will be performed using the variable.

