7.4.1. Primary Analysis: Reduction in Use of Antihypertensive Medication

The primary endpoint for this trial is the proportion of study subjects with a reduction (including discontinuation) of all antihypertensive medication by at least 50% for at least six months or two cycles of iobenguane I 131. The 50% reduction is determined separately for each baseline medication, based on the total daily dose of the antihypertensive medication(s) on the day of the first therapeutic dose.

A benefit duration period is measured by maximum duration as follows. The benefit duration period commences when the subject's medication is reduced to a level below 50% of baseline, and continues until the subject's medication rises above 50% of baseline, until the onset of a new antihypertensive medication of >14 days' duration, or to the last subject date as described in section 7.4.2, Primary Endpoint Calculation. A benefit duration period must begin during the 12-Month Efficacy Phase but may end during the Long-term Follow-up Phase. If the subject discontinues participation in the study before the Month 12 efficacy evaluation, the last date for calculation of the duration of benefit is the date of termination in the study.

For purposes of illustration, the following examples are provided (Month refers to the number of 28-day months after the first Therapeutic Dose).

- Example 1: A subject experiences the clinical benefit from the beginning of Month 2 to the beginning of Month 4, and then again from the beginning of Month 5 to the beginning of Month 12. Since the maximum duration of the benefit was 7 months, the subject is considered a success on the primary endpoint.
- Example 2: A subject experiences the clinical benefit from the beginning of Month 2 to the beginning of Month 4, and then again from the beginning of Month 6 to the beginning of

Month 11. Even though the subject experienced the clinical benefit for a total of 7 months, the maximum duration of the benefit was only 5 months, so the subject is considered a failure on the primary endpoint.

- Example 3: A subject experiences the benefit from the beginning of Month 2 to the beginning of Month 9. At Month 10, the subject receives another anticancer treatment and is discontinued from the study. Since the maximum duration of the benefit was 7 months, prior to discontinuation, the subject is considered a success on the primary endpoint.

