5. A long-term (i.e., duration > 14 days) increase in dose over the baseline dose of an existing antihypertensive medication regimen after receiving a therapeutic dose will not disqualify a subject from being able to achieve the primary endpoint if all antihypertensive medications are reduced to a level of 50% or below the baseline dose for at least six consecutive months in duration, since the increase may have been made before a tumor response was obtained. The introduction of a new antihypertensive medication with a duration of >14 days will be considered as the end of a benefit duration period. The start date for the duration of response is the date that the last antihypertensive medication is reduced to the level of 50% or below the baseline dose.
6. The introduction of an antihypertensive medication regimen or increase in existing antihypertensive medication regimen that occurs after the subject has already met the primary endpoint (i.e., had a $\geq 50\%$ reduction of all antihypertensive medications for at least six consecutive months) will not disqualify the subject from achieving the primary endpoint.

Calculation of Duration of Response

The six-month duration of the primary endpoint response begins on the date during the 12-Month Efficacy Phase when all baseline antihypertensive medications have been reduced by at least 50% and any new medications are discontinued (the date post-therapeutic dosing when the reduction of the last antihypertensive medication reduced by at least 50% or the new medication is discontinued) and ends once six consecutive months (i.e., 168 days) duration of sustained $\geq 50\%$ reduction has been achieved, regardless of the phase of the study during which the end date of the response occurs (i.e., 12-Month Efficacy Phase vs. Long-Term Follow-Up Phase).

The end date for which the duration of the $\geq 50\%$ reduction of all antihypertensive medications is determined as the earlier of:

- a. the date that the subject no longer meets the criteria of having a $\geq 50\%$ reduction of all baseline antihypertensive medications (i.e., the starting date of a new long-term continuing antihypertensive medication or a dose change in an existing regimen of antihypertensive medication that exceeds the $\geq 50\%$ reduction of the baseline dose that is greater than 14 days in duration and continues without a reduction to the $\geq 50\%$ level)

OR

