Table 14.2.4.1	EORTC QLQ-C30 Global Health Status/Quality of Life (Population: Full Analysis Set)
Table 14.2.4.2	EORTC QLQ-C30 Functional Scales (Population: Full Analysis Set)
Table 14.2.4.3	EORTC QLQ-C30 Symptom Scales (Population: Full Analysis Set)
Table 14.2.5A	NIH Pheochromocytoma Symptoms QOL Questionnaire: Pre Amendment 2 (Population: Full Analysis Set)
Table 14.2.5B	NIH Pheochromocytoma Symptoms QOL Questionnaire: Amendment 2 (Population: Full Analysis Set)
Table 14.2.6	Karnofsky Performance Status (Population: Full Analysis Set)
Table 14.2.7	Tumor Pain Medication Shift Table (Population: Full Analysis Set)

Table 14.2.8.1	Overall Survival (Population: Full Analysis Set)
Table 14.2.8.2	Overall Survival by Primary Endpoint Status (Population: Full Analysis Set)
Table 14.3.1.1	Treatment-Emergent Adverse Events (Population: Safety)
Table 14.3.1.1.1	Treatment-Emergent Adverse Events with Start Dates after Week 15 Following the Last Therapeutic Dose (Population: Safety)
Table 14.3.1.1.2	Treatment-Emergent Adverse Events with Start Dates after the Start of a New Anticancer Therapy but Prior to Week 15 for Subjects who Withdrew due to New Anticancer Treatment (Population: Safety)
Table 14.3.1.2	Treatment-Emergent Adverse Events by Grade (Population: Safety)
Table 14.3.1.3	Treatment-Emergent Serious Adverse Events (Population: Safety)
Table 14.3.1.4	Hematologic Serious or Grade 3/4 Adverse Events (Population: Safety)
Table 14.3.1.5	Grade 3/4 Adverse Events (Population: Safety)
Table 14.3.1.6	Adverse Events of Special Interest (AESI) (Population: Safety)
Table 14.3.2.1	Listing of Deaths During 12 Month Assessment Period (Population: Safety)
Table 14.3.2.2	Listing of Serious Adverse Events (Population: Safety)
Table 14.3.2.3	Listing of Adverse Events Leading to Drug Withdrawal (Population: Safety)
Table 14.3.2.4	Listing of Adverse Events of Special Interest (AESI) (Population: Safety)
Table 14.3.4.1.1	Change from Baseline in Hematology (Population: Safety)
Table 14.3.4.1.2	Change from Baseline in Chemistry (Population: Safety)
Table 14.3.4.1.3	Change from Baseline in Urinalysis Results (Population: Safety)
Table 14.3.4.1.4	Shifts in CTC Grade for Laboratory Parameters with Uni-Directional Criteria (Population: Safety)
Table 14.3.4.1.5	Shifts in CTC Grade for Laboratory Parameters with Bi-directional Criteria
Table 14.3.4.1.6	Incidence Rate of Post First Therapeutic Dose CTC Grade 3/4 Laboratory Values (Population: Full Analysis Set)

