APPENDIX 1. VISIT WINDOWS

These windows are intended for data summaries by time point. When multiple assessments fall within a window, the assessment closest to the nominal time will be used in summaries. If there are multiple visits equally distant from the midpoint of a window, then the earlier visit will be used.

Efficacy Assessments

No	End Point	From Imaging Dose 1	From Therapeutic Dose 1	From Therapeutic Dose 2
1	Overall Tumor Response (CT/MRI Scans)	Screening / Baseline (Day -28 to Day 0)	Month 3 (Day 81 - Day 101) Month 6 (Day 173 - Day 193) Month 9 (Day 264 - Day 284) Month 12 (Day 355 - Day 375) Month 18 (Day 518 - Day 578) Month 24 (Day 700 - Day 760) Month 30 (Day 883 - Day 943) Month 36 (Day 1065 - Day 1125) Month 42 (Day 1248 - Day 1308) Month 48 (Day 1430 - Day 1490) Month 54 (Day 1613 - Day 1673) Month 60 (Day 1795 - Day 1855)	
2	Tumor Markers	Screening / Baseline (Day -28 to Day 0)	Week 2 (Day 8 - Day 14) Week 4 (Day 22 - Day 28) Week 6 (Day 36 - Day 42) Week 8 (Day 50 - Day 56) Week 10 (Day 64 - Day 70) Week 12 (Day 78 - Day 84) Week 14 (Day 92 - Day 98) Week 16 (Day 106 - Day 112) Week 18 (Day 120 - Day 126) Week 20 (Day 134 - Day 140) Week 22 (Day 148 - Day 154) Week 24 (Day 162 - Day 168) Month 7 (Day 203 - Day 223)	

No	End Point	From Imaging Dose 1	From Therapeutic Dose 1	From Therapeutic Dose 2
			Month 8 (Day 233 - Day 253) Month 9 (Day 264 - Day 284) Month 10 (Day 294 - Day 314) Month 11 (Day 325 - Day 345) Month 12 (Day 355 - Day 375) Month 18 (Day 518 - Day 578) Month 24 (Day 700 - Day 760) Month 30 (Day 883 - Day 943) Month 36 (Day 1065 - Day 1125) Month 42 (Day 1248 - Day 1308) Month 48 (Day 1430 - Day 1490) Month 54 (Day 1613 - Day 1673) Month 60 (Day 1795 - Day 1855)	
3	Soloway Score (Bone Scan) and optional FDG-PET Scan	Screening / Baseline (Day -28 to Day 0)	Month 3 (Day 81 - Day 101) Month 6 (Day 173 - Day 193) Month 9 (Day 264 - Day 284) Month 12 (Day 355 - Day 375)	
4	Karnofsky Performance	Screening / Baseline (Day -28 to Day 0)	Day 1 Week 6 ± 10 days (Day 32 - Day 52) Month 3 (Day 81 - Day 101) Month 6 (Day 173 - Day 193) Month 9 (Day 264 - Day 284) Month 12 (Day 355 - Day 375)	Day 1 Week 6 ± 10 days (Day 32 - Day 52)

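### Overall survival from first dose split by primary-endpoint status (SAP Table 14.2.8.2) has guarantee-time bias that favours responders even with no true association

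*SAP*

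**What the plan says.** SAP 7.4.11 says that overall survival (OS) "is defined as the time from the date of first therapeutic dose to the date of death from any cause", with Kaplan-Meier rates at Years 1 to 5. It adds: "Overall survival will also be presented by primary endpoint status". SAP section 11 lists the output as Table 14.2.8.2, for the Full Analysis Set. SAP 5.3 keeps in that set everyone who received the first therapeutic dose.

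Primary-endpoint status depends on later events. Under SAP 7.4.2 the response period starts after dosing, once all baseline antihypertensives are at least halved, and "ends once six consecutive months (i.e., 168 days) duration of sustained" reduction has been reached. SAP 7.4.1 states: "A benefit duration period must begin during the 12-Month Efficacy Phase but may end during the Long-term Follow-up Phase". SAP section 7 fixes the window for starting: "For the purposes of defining the 12-month efficacy period in which the primary endpoint benefit could begin, this period is 12 calendar months". SAP 7.4.2 lists death during the efficacy phase among the dispositions that end the benefit period. The two-cycle wording gives no shorter route, because SAP 4.2 makes a cycle three months.

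Sections 7.4.11, 7.8, 7.9 and 11 contain no landmark, time-dependent method or caveat for this split. Both sensitivity analyses in 7.9 concern the primary endpoint only.

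**The concern.** The groups are defined by something that happens after the OS clock has started and that requires the subject to stay alive. Responders carry a stretch of follow-up in which, by definition, they cannot die. Every death in that stretch is assigned to the non-responders. This is guarantee-time (immortal-time) bias.

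The primary endpoint of this single-arm trial is medication reduction. A table in which responders live longer would naturally be read as support for that endpoint, and the table alone would not let a reader separate the artefact from a real link. The Year-1 rate by status is affected most.

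**Working it through.** **Guarantee time.** The SAP's own figure reproduces: 6 months × 28 days = 168 days. The earliest completion is Day 168. The latest start is about Day 365, so the latest completion is 365 + 168 = Day 533.

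**Survival inputs.** The documents give no early-death rate for this trial, so four levels from the protocol are used as assumptions:
- a median of 24 months (7.1 describes survival in progressive disease as often no longer than this);
- 5-year survival of 40% (7.1);
- 5-year survival of 64% (7.2, high-dose phase II series);
- 5-year survival of 85% (7.2, 15-patient series).

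**Other assumptions.** No true association; exponential survival; 25% potential responders (the alternative in SAP section 6); benefit onset uniform on Days 30 to 270; censoring at 5 years. Two cases:
- Case 1: nobody dies before Day 182, which reads the inclusion criterion on expected survival (protocol 9.5) as met by all. The 5-year levels are held fixed. The 24-month median is counted from Day 182, so it is about 30 months from first dose.
- Case 2: constant hazard from Day 0.

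**Formulas.** Let V = onset + 168, uniform on Days 198 to 438, and let S be the common survival function.
- Share counted as responders: 0.25 × E[S(V)].
- Responders alive at t: E[S(max(V, t))] / E[S(V)].
- Non-responders alive at t: (S(t) − 0.25 × E[S(max(V, t))]) / (1 − 0.25 × E[S(V)]).

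**Worked example: case 2, median 24 months (730.5 days), t = 365.25.**
- λ = ln 2 / 730.5 = 0.000949 per day.
- E[S(V)] = (e^(−198λ) − e^(−438λ)) / (240λ) = (0.8287 − 0.6599) / 0.2277 = 0.741. The responder share is 0.25 × 0.741 = 0.185.
- E[S(max(V, t))] = 0.6999, so responders: 0.6999 / 0.741 = 94.4%.
- S(t) = 0.7071, so non-responders: (0.7071 − 0.1750) / (1 − 0.1853) = 65.3%.
- Gap: 29.1 points, with no association built in.

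**All levels** (gaps from unrounded values; the event-rate ratio is deaths per person-time to 5 years, responders over non-responders, by simulation of 2,000,000 subjects):

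| Case | Survival level | 1-year OS, resp. vs non-resp. (%) | Gap (points) | Event-rate ratio |
|---|---|---|---|---|
| 1 | 24-month median | 94.4 vs 81.1 | 13.3 | 0.84 |
| 1 | 40% at 5 years | 96.7 vs 88.3 | 8.4 | 0.86 |
| 1 | 64% | 98.4 vs 94.1 | 4.3 | 0.88 |
| 1 | 85% | 99.4 vs 97.8 | 1.6 | 0.89 |
| 2 | 24-month median | 94.4 vs 65.3 | 29.1 | 0.66 |
| 2 | 40% at 5 years | 97.1 vs 79.5 | 17.6 | 0.72 |
| 2 | 64% | 98.6 vs 89.3 | 9.3 | 0.75 |
| 2 | 85% | 99.5 vs 95.9 | 3.5 | 0.77 |

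At 5 years the gap is 1.5 to 4 points in case 1 and 3 to 9 in case 2. Cox hazard ratios are 0.82 to 0.89 and 0.66 to 0.77.

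**Sensitivity.**
- Onset on Days 30 to 120: Cox hazard ratio 0.91 to 0.95 (case 1), 0.72 to 0.83 (case 2).
- Onset on Days 90 to 365: 0.74 to 0.82, 0.60 to 0.72.
- Responder share 10%: event-rate ratio 0.86 to 0.91, 0.70 to 0.80.
- Responder share 40%: 0.81 to 0.86, 0.61 to 0.73.

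**One trial of 58.** Responders look better in 58 to 71% of simulated trials (case 1) or 65 to 89% (case 2). A nominal two-sided log-rank p < 0.05 appears in 3 to 7% or 3 to 14%.

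**Do the remedies work?** Under the same null, a Day 548 landmark and a Cox model with time-dependent response each give hazard ratios of 0.99 to 1.01, in both cases and all three onset windows.

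**The case against.** The strongest reply is that this is one descriptive table: no test, hazard ratio or claim is planned, so a footnote would be enough. The SAP also plans subject-level listings of survival, medication dates and day of death, from which the landmark split could be rebuilt. The size rests on assumed onset times and an assumed survival shape. The 29-point gap needs the poorest prognosis together with about 15% dead by Day 168, which sits badly with an entry criterion of at least six months' expected survival. With that criterion met and 5-year survival of 64 to 85%, the 1-year gap is only about 2 to 4 points.

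Much of this stands as a limit on importance. The size is uncertain, may be small, and in a single trial of 58 the direction can differ. It does not make the table sound. The direction in expectation follows from the SAP's definitions whenever some deaths precede completion. The entry criterion is a physician's prognosis, and even if everyone met it, completion can run to Day 533. A footnote warns of the artefact but supplies no unbiased comparison, and readers should not have to rebuild one from listings.

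**Conclusion.** The concern holds. As planned, Table 14.2.8.2 is biased in favour of responders in expectation, with no safeguard in the SAP. Under the stated assumptions the event-rate ratio with no true association is 0.84 to 0.89 if nobody dies before Day 182 and 0.66 to 0.77 under constant hazard. The size depends on survival, onset and responder share, none of which the documents fix for this trial; the direction in expectation does not. The table should be changed, but the primary endpoint analysis and the overall OS curve are unaffected.

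**What to change.** For Table 14.2.8.2, do one of the following.

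- **Landmark.** Present OS from a fixed day at or after Day 533, among subjects alive and in follow-up, by responder status on that day. Day 548 fits the SAP: it is the centre of the Month 18 window in Appendix 1, (518 + 578) / 2. For Kaplan-Meier OS the SAP says "a month will be defined as a calendar month or 30.25 days", which puts Month 18 at 18 × 30.25 = Day 544.5, also after Day 533. A Day 168 landmark would be too early, because response can be completed later.
- **Time-dependent response.** Fit a Cox model in which response switches on when the 168 days are completed, shown with Simon-Makuch curves. Do not substitute crude person-time rates: in case 1 they give 1.16 to 1.28 where the truth is 1.

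If the unadjusted split is kept, show it only beside one of these, with a footnote on the guarantee time. If OS is also shown by number of therapeutic doses (SAP 7.8), compare one dose with two from a landmark after the protocol's 24-week limit for the second dose (10.2), since the same problem arises there.

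**Cost.** SAP wording and reprogramming of one table; no new data. The Day 548 landmark drops earlier deaths, about 4 to 29% of subjects in case 1 and 5 to 41% in case 2. Of 58, about 41 to 56 or 34 to 55 remain. Responders among them number about 10 to 14 or 9 to 14 at a 25% share, but only about 4 to 6 or 3 to 6 at 10%. Subjects no longer followed are also lost. The landmark gives conditional survival and no Year-1 rate by status; the time-dependent model drops nobody. Neither removes selection through progression or new anticancer therapy ending the benefit period (SAP 7.4.2), so the comparison remains an association.

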7.4.12. Site Assessment of Disease

A clinical assessment of subject status is performed during office visits. This information will be provided in a data listing.

7.4.13. Viable Tumor Tissue (exploratory)

Results of FDG PET assessments will be listed for those subjects who underwent the scans.

7.5. Safety

Safety analyses will include TEAEs, clinical laboratory measurements, vital signs measurements, ECGs, and physical examination findings. The Safety Set will be used in all analyses of safety. However, those in the Safety Set who are lacking follow-up for safety will not be included when computing incidence of AEs, because their inclusion would dilute the percentages of subjects with AEs or laboratory toxicities.

7.5.1. Adverse Events

TEAEs are defined as AEs whose onset dates are on or after the first administration of any amount of study drug to the end of 15 weeks after the administration of the last therapeutic dose of iobenguane I 131. If the onset date is incomplete, then assessment will be made based on available information (i.e., comparing available onset month and year). If the onset date is incomplete and assessment could not be made based on the available information (for example, year is missing) then the AE will be considered as TEAE. Events that resolve prior to date of the first dose of study drug will not be considered as TEAEs regardless of completeness of the onset date. In all table summaries, only TEAEs will be presented. All AEs will be presented in listings, regardless of whether they are treatment-emergent.

All adverse events that are neither serious adverse events nor adverse events of special interest reported with start dates on or after the first day of week 16 following the last therapeutic dose will be presented in a summary table and will be included in the listing of all adverse events.

For subjects who discontinue participation in the study due to receiving another anticancer therapy, all adverse events reported with start dates after the initiation date of the new therapy but prior to the last day of week 15 after the last therapeutic dose will be summarized separately. These events will also be included in the overall adverse event summaries. These events will be flagged in the listings of adverse events.

AEs were originally coded according to system organ class and preferred term using MedDRA version 12, and were recoded to MedDRA version 19.1 for analysis. The AE terms were graded for severity according to the Common Terminology Criteria for Adverse Events v3.0 (CTCAE v3).

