11.5.2 Adverse Events

Non-serious adverse events and serious adverse events are defined in Section 12. Data will be collected for any non-serious or serious adverse events that occur from the time of signed informed consent through a Safety Phone Call at 16 weeks after the last therapeutic dose. If the timepoint of the 16 week Safety Phone Call falls within 2 weeks of a scheduled visit, the AE/SAE assessment can be performed at that visit instead of through a Safety Phone Call. The Investigator will contact the subject via telephone or follow-up by other appropriate means at six weeks following each Therapeutic Dose of Ultratrace iobenguane I 131 if the subject does not return for a safety visit. All adverse events will be recorded in the AE section of the CRF as specified in Section 12. Only post-dose untoward medical events will be assessed as relevant to the safety profile of Ultratrace iobenguane I 131. As part of long-term follow-up, data on occurrence of adverse events of special interest (Appendix VI) will be collected as described in Section 12.

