12.1.4 Data Collection

The Investigator will elicit information through non-leading questioning and examination of the subject about the occurrence of adverse events from the time of informed consent until the Safety Phone Call 16 weeks after the last dose of study drug.

For each event, the following information will be recorded in the subject's records and transcribed onto the AE section of the CRF according to the instructions described below.

- Classification of the Event as serious or non-serious: Classify the event as either serious or non-serious (see definitions in Section 12.1.1).
- Classification of the Event as an adverse event of special interest (AESI): Determine if the event is an AESI (see Appendix VI).
- **Description of Signs or Symptoms**: Whenever possible, record a specific diagnosis for the event. If a diagnosis cannot be made, then record each sign or symptom separately, (e.g., record nausea and vomiting as two events).
- **Onset Date and Time:** Record the date and time the event started (e.g. if a laboratory test is reported as an AE, record the start date as the date of collection of the first lab sample that shows the change.)
- Stop Date and Time: Record the date and time the event resolved.
- **Grade:** Refer to the common terminology criteria for adverse events (CTCAE, version 3).

Relationship to the Study Drug: Make every effort to evaluate the relationship between the study drug and the AE as determined by the investigator per the definitions below:

RelatedThe event is reasonably suspected of a causal relationship to the
study drug and/or causality cannot definitively be ruled out.Not RelatedThe event is definitely due to causes separate from the
administration of the study drug, i.e.,

- documented pre-existing condition
- technical and manual procedural problems
- concomitant medication
- subject's clinical state

• Action Taken with Study Drug:

- 1. Dose not changed (no action taken)
- 2. Dose reduced
- 3. Drug withdrawn
- 4. Not applicable

• Adverse Event Outcome:

- 1. Recovered/ Resolved without sequelae
- 2. Recovered/Resolved with sequelae
- **3.** Not recovered/Not resolved, event is on-going at the end of the AE collection period.
- **4. Death (fatal)** the event description must be the primary cause of death. Disease progression is not considered an acceptable cause of death for purposes of this study.
- 5. Unknown

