13.1 Analysis Sets

Figure 2 is a flow diagram of the protocol defined analysis sets. The Enrolled Set includes all subjects who have provided signed informed consent. The Dosimetry Set and Safety Set include all subjects who received the Imaging Dose. Adverse Events prior to the Imaging Dose will be captured for all enrolled subjects and reported separately from treatment-emergent AEs. The Full Analysis Set is a subset of the Dosimetry Set / Safety Set, excluding subjects who did not receive at least the first Therapeutic Dose. Subjects whose therapeutic dose is decreased below studv 500 mCi. based on results of the dosimetry or hematological dose modifications are included in the Full Analysis Set. The Full Analysis Set will be used for the primary analysis of efficacy. The Per Protocol Set is a subset of the Full Analysis Set, excluding subjects who received only one Therapeutic Dose, who did not attend the 3 Month and 6 Month Efficacy Visits, or with major protocol violations. Major protocol violations are defined as those that could impact the efficacy evaluation such as a subject is ineligible, missing key data, received an unauthorized treatment, etc. Only subjects receiving both Therapeutic Doses and with sufficient follow-up for efficacy will contribute to the Per Protocol Set. Key efficacy endpoints, including the primary endpoint of the proportion of subjects experiencing a reduction in use of all antihypertensive medication for at least six months or two cycles, will be analyzed on the Per Protocol Set (in addition to the Full Analysis Set).

FIGURE 2: SCHEMATIC OF PROTOCOL DEFINED POPULATIONS

* Adverse Events prior to the Imaging Dose will be captured for all enrolled subjects and reported separately from treatment-emergent AEs.

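### An adverse event that starts between consent and the Imaging Dose, stays on one record and worsens after dosing is missing from the AE summary tables

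*SAP*

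**What the plan says.** SAP 7.5.1 sets the rule: "TEAEs are defined as AEs whose onset dates are on or after the first administration of any amount of study drug", with the window closing at the end of week 15 after the last therapeutic dose. It then says "In all table summaries, only TEAEs will be presented", while "All AEs will be presented in listings, regardless of whether they are treatment-emergent". Its one explicit rule for events that began before dosing concerns those already over: "Events that resolve prior to date of the first dose of study drug will not be considered as TEAEs". An onset date too incomplete to be placed makes the event a TEAE by default.

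Protocol 11.5.2 starts collection earlier: "Data will be collected for any non-serious or serious adverse events that occur from the time of signed informed consent". Protocol 12.1.4 asks for an onset, a stop and a grade for each event; for the onset the instruction is "Record the date and time the event started". Protocol 13.1 keeps pre-dose events apart: "Adverse Events prior to the Imaging Dose will be captured for all enrolled subjects and reported separately from treatment-emergent AEs".

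**The concern.** Collection starts at consent and counting starts at the first dose, so some events will be open when dosing begins. For those that continue and then get worse, the SAP has no rule beyond onset date, and onset date places them outside the tables whatever grade they later reach.

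What is at stake is the frequency and severity of individual terms in the safety tables. The omission runs in one direction: leaving out a worsened event can lower a rate but never raise one. With no control arm, the same omission on another arm cannot offset it. Elsewhere the SAP resolves uncertainty against the drug: an onset that cannot be placed counts as treatment-emergent, a missing relationship is tabulated as related (7.5.2), and a missing severity is tabulated as grade 3 (7.5.3). Events that persist and worsen do not receive that caution.

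**Working it through.** No arithmetic applies, because the documents state no figure on this point. The check is to follow a record through the rules.

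**1. When the exposed window opens and closes.** It opens at consent (Protocol 11.5.2). It closes at the first study drug of any amount, which is the Imaging Dose. Protocol Appendix VII schedules screening from Week -4 to the Imaging Dose, so the window is about four weeks.

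**2. Four kinds of record under SAP 7.5.1.**
- Known onset before the Imaging Dose, one continuing record, higher grade after dosing: not a TEAE, listings only.
- Worsening entered as its own AE after dosing: post-dose onset, so a TEAE if within the end window.
- Onset after the Imaging Dose but before therapy: already a TEAE.
- Onset that cannot be placed: a TEAE, unless the event resolved before the first dose.

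Only the first kind is lost.

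**3. Whether another table recovers it.**
- Relationship (SAP 7.5.2) and severity (7.5.3), including the grade 3/4 tabulations and the common-event chart, are built from TEAEs: no.
- The late-event table takes non-serious, non-AESI events "reported with start dates on or after the first day of week 16 following the last therapeutic dose will be presented in a summary table". It also works by start date: no.
- The AESI summary (7.5.8) requires onset beyond 16 weeks after the last therapeutic dose: no.
- The tabulation of serious events (7.5.4) is of treatment-emergent SAEs: no. However, 7.5.4 also provides a listing of all SAEs, planned as Table 14.3.2.2, so an event that becomes serious is displayed there.
- Laboratory shift tables (7.5.9) run from baseline to worst post-Screening grade whatever the AE onset: yes, for graded laboratory parameters.

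**4. Whether the recording rules move events from the first kind to the second.** Protocol 12.2.1 and 12.3 to 12.5 tell the investigator to evaluate pre-dose to post-dose worsening in laboratory tests, ECG, physical examination and vital signs, and to record it on the AE form if it meets the AE definition. Protocol 12.1.4 dates a laboratory AE from the first sample showing the change, which gives a post-dose onset. No comparable instruction covers symptoms. Neither document says whether a grade increase in a symptom already on record opens a new one.

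**5. Size.** The count would be the number of subjects, times the share with an AE open at the Imaging Dose, times the share of those whose AE worsens on the same record. The documents plan about 75 enrolled subjects and give neither share, so no estimate is possible.

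**The case against.** The strongest answer is that most toxicity of interest does not pass through this gap. Qualifying worsening in four categories is to be recorded as an AE, and laboratory changes carry a post-dose date. Marrow toxicity is therefore largely covered, and the shift tables show it again. This stands. A reader might infer that worsened events vanish from every adverse-event table, hematologic ones included; the documents do not support that.

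A second answer is that the population's existing symptoms are not the exposed group. Symptoms present before consent belong to medical history (Protocol 11.5.1), and AE collection covers events occurring from consent. A later worsening reported as an AE would have a post-dose start. This also stands: a reader might take the rule to exclude worsening of baseline disease symptoms generally, but it reaches only AEs that newly begin between consent and the Imaging Dose.

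Third, the CRF Completion Guidelines named in Protocol 15.5.2 may already say how a grade increase is recorded. They are not available here. If they require a new record, the gap closes. That is a reason to check, since the two documents that define the analysis do not say so.

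Finally, the overall any-TEAE rate may hardly move. In the earlier MIP-IB12 study all 21 treated patients had a treatment-related TEAE (Protocol 7.6.2). That is fair; any effect would be on individual terms and grades.

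**Conclusion.** The point holds in a narrow form. An AE that begins between consent and the Imaging Dose, is carried as one record with a known onset, and increases in grade after dosing is absent from the TEAE, relatedness and grade 3/4 summaries. It remains in the listings and, if serious, in the all-SAE listing. The cases affected are mainly symptomatic.

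This rests on two assumptions: that at least some sites kept a worsening symptom on its existing record, and that no CRF instruction outside these documents prevented it. A reader might be tempted to attach a percentage of subjects, but nothing in the documents supports one. The number is probably small, because the window is short and only new events count. The direction is certain: the rule can only understate.

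**What to change.** In SAP 7.5.1, extend the definition so that an AE with onset before the first dose is also treatment-emergent if it increases in CTCAE grade or becomes serious on or after the first dose, within the existing end window. Tabulate it at its worst post-dose grade. Add a line noting that such an event may also appear in the separate pre-dose reporting described in Protocol 13.1.

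Before database lock, query the AEs that were open at the Imaging Dose to establish whether and when each worsened. Where the timing cannot be established, count the event as a TEAE, in line with the existing rule for onset dates that cannot be placed. Sites need not split old records retrospectively; with enrollment completed in December 2015 (SAP 4.1), that would be more work than the point justifies.

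The cost is one sentence in the SAP, a small data query, and slightly less favourable rates for some terms or grades. If sites already entered worsening as separate events, subject-level counts should not change.
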